In routine care in this setting, viral load tests are to be repeated every three months in pregnancy and every six months during breastfeeding, so we expect that most women will have a routine viral load completed before six months postpartum. To avoid additional blood draws for the participant, at the follow-up visit, the study staff will check NHLS to determine the most recent viral load test. If the participant has had no viral load test within 3 months prior to the six-month study follow-up visit, a blood draw for viral load will be conducted by the clinical staff at the Gugulethu CHC. A clinic nurse will collect 5 ml of venous blood, which will be transported daily to the National Health Laboratory Services (NHLs) for HIV viral load testing (Abbott Molecular RealTime HIV-1 assay (Abbott Molecular, Illinois, USA). We will not recontact participants about viral load results unless participants are on ART and the viral load result indicates lack of viral suppression. In that case, results will be made available to participants over the phone (or in person, at participant's wish) with appropriate referrals. For all participants, viral load results will be captured using the participants provincial folder number into the NHLs database, as is standard practice for routine laboratory results in South Africa.

Uninstall app

During the follow-up visit, the CareConekta app will be uninstalled from each participant's phone.

Reimbursement

After all the above steps are complete, the enrollment visit will conclude with providing the participant R150 reimbursement for transport and missed opportunity costs. Payment will be made in cash and/or grocery vouchers and will be recorded in a reimbursement log.

File review activities

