Electronic and paper files will be reviewed after the participant's final visit to assess engagement in HIV care. If the participant fails to return for a final visit, files will be reviewed a minimum of seven months after estimated delivery. Electronic data on health facility visits and pharmacy dispensing, including facility recorded deaths, will be requested the Provincial Health Data Centre of the Western Cape Department of Health by providing a list of folder numbers of women who have consented and enrolled in the study. These data include all public health facilities in the Western Cape Province, which is the location of the study site. Laboratory records, including viral loads, from any South African facility will be abstracted from the NHLS database. Participants in both arms who are lost from the study at the time of study close will be traced through staff outreach and electronic/paper medical records. Informed consent will include permission to link with electronic medical records.

Table of schedule of measures

Item for completion	Enrolment	Early postpartum phone call	6 months postpartum
Eligibility Checklist	x		
Informed Consent	x		
Linkage form	x	x child details	
Randomisation log	x		
Demographics and medical history	x		x
Maternal mobility (past and planned)	x		x
Maternal clinic switching	x		x
Perceived barriers and facilitators of engagement in care	x		x
Depression (PHQ-4)	x		x
Alcohol and drug use (AUDIT-C and DUDIT Q1)	x		x
Patient provider relationship scale	x		x
ART adherence	x		x
WHO VAW (intimate partner violence)	x		
Social impact scale (stigma)	x		
Availability of social support	x		
Life events (trauma)			x
Infant health			x
Child mobility			x
Acceptability of CareConekta			x
Impact of COVID-19 & lockdown of HIV care and mobility			x
Laboratory tests			
HIV viral load*			x
Record review			
Antenatal and obstetric information	x	x	x
ART pharmacy records	x	x	x
Maternal laboratory results	x	x	x
Child HIV testing		x	x

* If no routine viral load result found in the three months before the study visit

DATA COLLECTION AND STORAGE

Data collection methods

Data will be collected in three ways:

- Face-to-face enrollment and follow-up questionnaires

- Medical record review (electronic and paper file records) to determine participant engagement in HIV care
- Electronic app usage and mobility data

Questionnaire data

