Aim 2b. To evaluate the initial efficacy of the enhanced CareConekta intervention, using notifications and staff contact to improve engagement in HIV care, by assessing the association between study arm and engagement in HIV care at six-months postpartum.

Outcome: Efficacy of the intervention

The overall efficacy analysis will include participants in both arms (n=200). To assess overall cohort engagement in HIV care, we will report retention in care, which will be assessed at the six-month postpartum point and defined as no documented HIV-specific contact with any healthcare facility (including medication pick-ups) for >3 months. We also will report viral suppression six months after delivery based on the viral load test closest to the six-month period, using thresholds of ≤50 and ≤1000 copies/ml. Additionally, we will report vertical HIV transmission and completion of the routine 10-week infant PCR test.

Study arm assignment is the primary exposure of interest. We will use Cox proportional hazard regression models to estimate the association of study arm assignment on these outcomes, and will produce adjusted hazard ratios and 95% confidence intervals for retention in care and achieving viral suppression by study arm. We also will identify other predictors of engagement in HIV care. We will produce crude Kaplan-Meier curves to time to loss to follow-up and time to viral suppression by study arm. In a secondary analysis, we will perform an as-treated analysis using self-reported data regarding actually reading the notifications and/or WhatsApp messages or staff phone calls to analyze the effect of receiving the intervention.

HUMAN SUBJECTS' PROTECTION

Ethical review process

The research protocol will be reviewed by the Institutional Review Boards at Vanderbilt University; the University of California, San Francisco; and the University of Cape Town in South Africa. All research activities will occur in South Africa. All procedures will conform to U.S. and South African ethical standards for human subjects' research.

Informed consent

Informed consent will be obtained for all participants as described in the "Informed Consent" section above.

Privacy and confidentiality

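### The retention rule does not exclude contacts that the study creates, so the six-month study viral load draw can score a woman who is out of care as retained

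*Combined protocol and SAP*

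**What the plan says.** The outcome text under Aim 1b and Aim 2b (Analysis plan and study outcomes) uses one rule for retention: "no documented HIV-specific contact with any healthcare facility (including medication pick-ups) for >3 months". It is to be "assessed at the six-month postpartum point". As worded, the rule describes loss rather than retention; I read it as the definition of not being retained.

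The six-month visit is offered to every participant, in care or not, with at least three attempts by phone or home visit (Recontacting participant). Under Viral load testing and potential blood draw: "If the participant has had no viral load test within 3 months prior to the six-month study follow-up visit, a blood draw" follows. It is not done by study staff: "a blood draw for viral load will be conducted by the clinical staff at the Gugulethu CHC". The result is "captured using the participants provincial folder number into the NHLs database, as is standard practice for routine laboratory results".

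File review activities places the record review after the "final visit to assess engagement in HIV care". It draws on facility visits, pharmacy dispensing and NHLS laboratory records, including viral loads. Women who do not return have their files reviewed at least seven months after estimated delivery.

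Both aims also plan Cox models and Kaplan-Meier curves of time to loss to follow-up.

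**The concern.** A viral load draw by a clinic nurse at a community health centre fits the wording of the retention rule: it is HIV-specific, documented and made at a healthcare facility. For some women it exists only because the study called them back. If it counts, the retention outcome partly measures who came to the study visit.

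Three results are at stake. Loss from care would be understated, and the Sample Size section says the pilot is meant to inform the size of later trials. True differences by arm (Aim 2b) or mobility (Aim 1b) would shrink. And if one group attends in person less often, a difference could appear without any difference in care.

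**Working it through.** **Step 1: does the draw reach the women who matter?** The draw is triggered by no viral load test in the 3 months before the visit. The loss rule needs no HIV-specific contact for more than 3 months. If a viral load test is itself such a contact, a woman past the loss threshold has no test in that window. If she attends in person, she meets the trigger. The trigger also catches women in care, because routine testing is six-monthly during breastfeeding; their status does not change.

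**Step 2: does the draw change her status?** The plan allows three readings.

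- *Status looked back from six months, visit on or before that point.* The draw falls inside the last 3 months, closes the gap, and she is scored as retained.
- *Any gap of more than 3 months is a dated loss event*, as time-to-loss curves imply. With last contact at month 2.5 and the draw at month 6, the gap is 6 − 2.5 = 3.5 months. She is already lost, and the draw changes nothing.
- *Status at the exact six-month date, visit later.* The draw is outside the window and harmless.

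The wording about assessment at six months favours a status reading; the Kaplan-Meier plan favours the second. No visit window or contact cut-off is given. If the proportion retained used the first reading and the curves used the second, the same woman would be retained in one analysis and lost in the other.

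**Step 3: size under the first reading.** The plan gives no figure to reproduce, and it states that no formal sample size estimation was made. Inputs:

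- p, the true proportion out of care. I assume 25%, close to the 25.2% lost at one year in an earlier cohort cited in the Introduction. The Introduction also cites 47.9% lost within six months of delivery, used here as an upper illustration.
- f, the share of out-of-care women who attend and are bled on or before the cut-off. The documents give no value, so this is assumed.

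Scored loss = p × (1 − f):

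| p | f = 0 | f = 30% | f = 50% | f = 70% |
|---|---|---|---|---|
| 25% | 25% | 17.5% | 12.5% | 7.5% |
| 47.9% | 47.9% | 33.5% | 23.95% | 14.4% |

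**Step 4: differences between groups.** With equal f, the scored difference is the true difference × (1 − f). An assumed 30% against 20% shrinks from 10 points to 10 × 0.5 = 5 points (f = 50%) or 10 × 0.3 = 3 points (f = 70%).

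With no true difference but unequal f, the false difference is p × (f₁ − f₂). For Aim 1b, assume p = 25% in both groups, f = 60% in non-travellers and 30% in travellers. Scored loss is 25% × 0.4 = 10% against 25% × 0.7 = 17.5%, a false mobility effect of 7.5 points.

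**The case against.** The strongest reply is that no sentence says the draw counts. The only contact named as an example is the medication pick-up. The file review lists laboratory records separately from visits and dispensing. The footnote to the schedule of measures shows that the team separates routine from study viral loads. This stands in part: the plan leaves the point open rather than directing the error. But the pick-up is given as an inclusion, not a limit, and the draw is also an in-person encounter with clinic staff.

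Second, the planned time-to-loss analysis may protect the result, and visits may often fall after six months, since recontact begins then and may take several attempts. Both points stand. The value of f could be near zero, and the illustrations above apply only under the first reading.

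Third, a reader might infer that the draw would create a false benefit for the intervention arm. The documents give little support for this. Recontact is the same in both arms, and extra staff contact goes only to intervention women who pass the travel threshold. If out-of-care women travel at the expected 25% and only travellers' attendance changes, an arm gap of 60% against 40% in f needs a gap of 0.20 / 0.25 = 80 points among travellers. The mobility comparison is more exposed, because a woman far from the site may complete the questionnaire by phone and have no draw.

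A reader might also take retention to be the main outcome, or women without a recent viral load to be mostly disengaged. Aim 2b lists its outcomes without ranking them, and six-monthly routine testing means that many of these women may be in care.

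**Conclusion.** The retention rule leaves open whether study-created contacts count and where the 3-month gap is anchored. Applied literally as status at six months, it scores an out-of-care woman as retained if she attends and is bled by the cut-off. Scored loss then falls in proportion to f: from an assumed 25% to between 17.5% and 7.5% for f between 30% and 70%. Differences shrink by the same factor if attendance is equal and are distorted if it is not, most plausibly by mobility in Aim 1b.

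The stronger conclusion, that the plan does count the draw and that attenders are therefore scored as in care, is not supported. It fails if an earlier gap is a loss event, if the visit is after the cut-off, or if follow-up is by phone only. Viral suppression is not affected. I rate this as should-fix, with moderate confidence.

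**What to change.** In the retention definition for Aims 1b and 2b:

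- State that the six-month study visit, its study-requested viral load draw, and facility contacts arising from that visit's referral or from end-of-study tracing do not count as HIV-specific contact.
- State that facility contacts during follow-up still count, including those prompted by intervention notifications, calls or messages. These are the effect that Aim 2b tests.
- Give one cut-off date for the gap of more than 3 months, used in both the six-month status and the time-to-loss analyses, and say whether a gap that closes before that date is a loss.

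Flag each study-requested draw with its date on the CRF, so that the matching NHLS record can be removed. Report a sensitivity analysis with and without other facility contacts on the study-visit day, since a same-day pick-up may be genuine. Keep the study draw for viral suppression.

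The cost is a few sentences, one CRF field and one extra analysis, settled before file review. The downside is that reported retention may be slightly lower.

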All women who meet the eligibility criteria and are interested in participating in the study will undergo written informed consent, which will be available in English and isiXhosa. The consent form will confirm the eligible woman’s understanding of the study procedures and her informed willingness to participate. The key messages of the informed consent process will include: 1) a description of the study goals and procedures, 2) voluntary participation in the study, 3) confidentiality and privacy with use of the app and study data, 4) the right to withdraw at any time, and 5) the standard of care received at the MOU or any other healthcare facility will not differ according to participation in the study. Specifically, we will request written informed consent for installation of the app, location tracking, data collection, medical record review (participant and infant), one blood draw, and re-contacting by study staff.

Once the consent form has been explained to the participant, any questions she may have will be answered. If the participant agrees to provide consent for participation, she will indicate this with her signature on the consent form. If she does not wish to participate or does not provide her consent for all the activities, she will not sign the consent form and will not be enrolled. A second copy of the form will be provided for her to sign as well and keep. The study staff member who administered the form will provide his or her name, signature and date as a witness to the signing. Signed informed consent forms will be stored in binders within a locked office and only accessible by study staff.

Linkage information and study ID assignment

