To assess engagement in HIV care, we will report retention in care, which will be assessed at the six-month postpartum point and defined as no documented HIV-specific contact with any healthcare facility (including medication pick-ups) for >3 months. We also will report viral suppression six months after delivery, using thresholds of ≤ 50 and ≤ 1000 copies/ml. Additionally, we will report vertical HIV transmission and completion of the routine 10-week infant PCR test.

We will fit a series of models of mobility metrics on outcomes. For one, we will use a dichotomous exposure of mobility (any travel >50 km: yes/no), we will use Cox proportional hazard regression models to estimate the association of mobility on these outcomes, and will produce adjusted hazard ratios and 95% confidence intervals for retention in care and achieving viral suppression. We also will identify other predictors of engagement in HIV care. We will produce crude Kaplan-Meier curves to time to loss to follow-up and time to viral suppression by mobility group. Additionally, we will perform sensitivity analyses to explore how the estimated effect size changes when using varying cut-off points to define mobility.

Aim 2a. To assess the acceptability and feasibility of the standard and enhanced app, with a focus on identifying user preference and implementation outcomes.

Outcome: Acceptability and feasibility of CareConekta

Acceptability and feasibility data will be collected among all 200 participants. Those in the intervention arm will receive additional questions related to the enhanced app features. The outcomes selected for analysis in Aim 3a correspond with the Technology Acceptance Model for Resource-Limited Settings (TAM-RLS) framework, which was designed to draw attention to end-user acceptability as a predictor of mHealth technology adoption in low-resource settings.⁴⁶ We will report proportions and 95% confidence intervals for categorical variables and medians and interquartile ranges for continuous variables. For open-ended questions, we will create a list of categorical themes that emerge over multiple readings and calculate the proportions for the response categories. We will select key illustrative quotes for each theme.

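### In Aim 1b some travellers are classed as exposed by a trip that began after the viral load on which they are scored

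*Combined protocol and SAP*

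**What the plan says.** The section on viral load testing at the six-month visit gives a reason and a rule. The reason: "To avoid additional blood draws for the participant, at the follow-up visit, the study staff will check NHLS to determine the most recent viral load". The rule: blood is drawn for the study "If the participant has had no viral load test within 3 months prior to the six-month study follow-up visit". The footnote to the schedule of measures repeats it: "If no routine viral load result found in the three months before the study visit". The consent section already covers "one blood draw".

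The same section describes routine practice: "viral load tests are to be repeated every three months in pregnancy and every six months during breastfeeding". From this the authors conclude that "we expect that most women will have a routine viral load completed before six months postpartum". They do not say what share will have a result inside the 3-month window.

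Aim 2b scores "viral suppression six months after delivery based on the viral load test closest to the six-month period". Aim 1b gives no rule for choosing the test: "We also will report viral suppression six months after delivery, using thresholds of ≤ 50 and ≤ 1000 copies/ml".

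Mobility data are collected for the whole of follow-up. Aim 1b uses a yes/no exposure (any travel beyond 50 km) in a Cox model restricted to the control arm. Its planned sensitivity analyses vary the cut-off that defines mobility. None varies the date or source of the viral load.

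**The concern.** Exposure and outcome are not ordered in time. Take a woman with a routine test 3.5 months after delivery who then travels, interrupts treatment and returns for the six-month visit. She has a result inside the window, so no study test is done. She counts as mobile because of the trip, yet her outcome was fixed before the trip began. Choosing the test closest to six months does not prevent this: unless a later routine test exists, the earlier result is the closest one available.

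The Cox model has the same weakness if travel enters as a fixed yes/no covariate, because later travel then classifies a woman at a test date that precedes it.

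There is a second, separate issue. Attenders with a result in the window are scored at varying times before the visit, and attenders without one are scored at the visit. Travel may change who has a recent routine test, so test timing can differ between the groups compared.

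The pilot is meant to inform the size of a later trial. What is at stake is the estimated association of travel with suppression that it passes on.

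**Working it through.** **Figures in the plan.** The Sample Size section expects 25% of 200 women to travel: 200 × 0.25 = 50, which reproduces its figure. Aim 1b uses the control arm only (100 women), so about 100 × 0.25 = 25 travellers. The window is 3 months. Follow-up is six months postpartum, or about nine months from enrolment in the third trimester.

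**Assumptions, not in the documents.** The age of an in-window routine test at the visit is uniform over 0-3 months (mean 1.5). Each traveller makes one trip, whose start is uniform over the last T months, with T = 6 (postpartum only) or T = 9 (all follow-up). A share r of travellers, 50-90%, has an in-window result. A test taken before the trip shows none of its effect, and a test taken after the trip starts shows all of it.

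**Share of trips that start after the test.** p = (mean test age) / T.
- T = 6: 1.5/6 = 0.25
- T = 9: 1.5/9 = 0.17
- Upper limit, every routine test a full 3 months old: 3/6 = 0.50 and 3/9 = 0.33

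**Travellers affected and dilution.** The affected share of travellers is r × p, which is also the proportional loss of the travel effect.

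| Case | p | r × p for r = 0.5 to 0.9 | of 50 travellers | of 25 in Aim 1b |
|---|---|---|---|---|
| Even tests, T = 6 | 0.25 | 0.125-0.225 | 6.3-11.3 | 3.1-5.6 |
| Even tests, T = 9 | 0.17 | 0.083-0.150 | 4.2-7.5 | 2.1-3.8 |
| Oldest tests, T = 6 | 0.50 | 0.25-0.45 | 12.5-22.5 | 6.3-11.3 |
| Oldest tests, T = 9 | 0.33 | 0.17-0.30 | 8.3-15.0 | 4.2-7.5 |

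With tests spread evenly, about 4-11 of 50 travellers are affected (2-6 of the 25 in Aim 1b), and the effect shrinks by about 8-22%.

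**Illustration.** Suppose true suppression is 85% in non-travellers and 65% in travellers (assumed). The 20-point difference becomes 20 × (1 − 0.083) = 18.3 to 20 × (1 − 0.225) = 15.5 points. At the extreme it is 20 × (1 − 0.45) = 11 points.

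**Direction of the timing difference.** Dilution pulls toward no effect. Unequal test timing need not. If suppression declines after delivery and travellers less often have an in-window result, travellers are tested later, at the visit, and look worse, which exaggerates the difference. If they more often have one, the reverse holds. The documents do not settle which applies.

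**The case against.** The rule is deliberate. It spares women a blood draw, it is the same in both arms, and the plan disclaims adequate power for Aim 2b. A study test for every attender would remove stale results, but if all 200 attend and 50-90% have an in-window result, it costs about 100-180 extra draws. That justifies the measurement rule. It does not justify counting later travel as exposure, which is an analysis choice and costs no blood.

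Several stronger readings are tempting, and the objection to each stands:

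- **That women in routine care get old tests and women out of care get fresh ones.** Routine testing in breastfeeding is six-monthly, so a fully engaged woman may have no result in the window and be drawn at the visit. The dividing line is having an in-window result. The fresh test also needs in-person attendance: the questionnaire may be done by telephone, and women who do not return have record review only.
- **That the main Aim 2b comparison counts later travel or notifications as exposure.** Its exposure is randomised arm, fixed at enrolment. Only the secondary as-treated analysis uses receipt of the intervention, so an exposure cut-off cannot correct the randomised estimate.
- **That both effects are biased toward the null.** Only the dilution has a clear direction.
- **That a quarter to a half of the effect is lost.** A quarter needs postpartum-only trips and an in-window result for every traveller. A half also needs every test to be a full 3 months old. The Introduction describes travel as typically following delivery. If trips cluster soon after delivery, fewer begin after the test. A woman with an earlier trip as well remains correctly exposed, and a trip begun days before the visit would hardly show even on a fresh test.

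A fresh draw only for women who travelled after their routine test may also look attractive. It would make test timing depend on exposure, which is the kind of imbalance at issue, so it is not recommended.

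**Conclusion.** The point holds for Aim 1b and for the as-treated part of Aim 2b. Followed as written, the plan can class a woman as exposed by a trip or contact that came after the viral load on which she is scored, and no planned analysis would reveal it.

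The size is modest: about 4-11 of 50 travellers and a dilution of about 8-22%, on assumed test timing, trip timing and in-window coverage. Since Aim 1b is an estimation aim with about 25 expected travellers, even 2-6 misordered women matter. The further bias from unequal test timing has unknown sign and size. The randomised comparison by arm does not misclassify exposure; its six-month outcome is simply a mixture of test times, which should be shown.

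**What to change.** - **Aim 1b, viral suppression:** state which viral load is used, and count only travel that began before its date, for example as a time-updated exposure in the planned Cox model.
- **Aim 1b, sensitivity analysis:** the cut-off gives earlier-tested women less time to be classed as mobile, so repeat the analysis with one common exposure window. For attenders, enrolment to about three months postpartum would serve (6 − 3 = 3), since no in-window or visit test should fall before that.
- **Aim 2b, as-treated:** count only notifications and staff contacts before the test used, dated as far as possible from the contact log and the time-stamped location data.
- **Aim 2b, randomised:** keep the comparison by arm with all women.
- **Both aims:** report test date, test age at six months and source (routine or study draw) by arm and mobility group. Add a sensitivity analysis limited to tests at or near six months, with the window fixed in advance.

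The location, contact and laboratory records needed are already collected, and no extra blood is drawn. The cost is a little more analysis work and somewhat fewer women classed as mobile for this outcome: about 2-6 of the 25 expected in Aim 1b on the assumptions above.
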